Safety data from approximately 250 participants implanted with the NT-501 device (nominal dose 20 ng/24 hours) suggest that adverse events (AEs) are generally limited to those related to the implant procedure. A number of participants have reported miosis, which is believed to be directly related to CNTF. During early development, a number of participants developed inflammation following implantation. This was subsequently related to impurities in the membrane. Trace to mild inflammation is seen postoperatively in a minority of participants and typically clears by 3 months. In the Phase 2 study, one episode of delayed inflammation (grade 3) was noted at 6 months and resolved by 12 months.

Studies of NT-501 in RP and AMD did not demonstrate any potential benefit. However, in the NTMT-02 study of 67 participants (99 eyes randomized 1:1) with MacTel, there was a statistically significant reduction in the rate of progression of MacTel in the eyes implanted with NT-501 as compared with the eyes that underwent the sham procedure. The mean (standard error [SE]) area of EZ break increased by 0.218 (0.049) mm² in the implanted eyes and by 0.270 (0.050) mm² in the sham eyes. The difference between groups in the increase of the MacTel lesion (0.052 mm²) was statistically significant ($p = 0.039$, 1-sided). The mean change in retinal sensitivity as measured by microperimetry was not different between the treated and sham eyes. However, when the aggregate retinal sensitivity (dB) was compared with the corresponding area affected by MacTel, a difference between treated and sham eyes was detected. This difference was consistent with the slower growth of the MacTel lesion in the treated eyes. There was a significant difference between treatment groups in reading speed at 24 months (13.5 words read per minute, $p = 0.016$). Specifically, the implanted eyes had not deteriorated from baseline (0.03 words read per minute), but the sham eyes showed impairment in reading speed relative to baseline (-13.5 words read per minute). The mean (SE) macular thickness was significantly increased in the treated population when compared with the sham group (NT-501: +5.45 [3.02] μ ; sham: -4.97 [2.85] μ ; $p = 0.007$). The mean (SE) pupil size was also significantly reduced in the implanted eyes as compared with the sham eyes (difference between groups: 0.922 [0.13] mm, $p < 0.0001$).

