12.3.2 Secondary Endpoint(s)

The secondary endpoints will be analyzed using the mITT population and the PP population to test for superiority of NT-501 over sham. The secondary endpoints are listed below:

- Mean change in aggregate sensitivity of microperimetry within the EZ line break area through 24 months
- Mean change in reading speed from baseline through 24 months
- Mean change in the NEI-VFQ-25 near activities subscale score from baseline through 24 months

Continuous secondary outcomes will be analyzed using a longitudinal mixed effects model and the corresponding 95% CI, SE, test statistic, and p-value of the difference between treatment group means at the 24-month time point will be computed. For the mixed effects model, fixed effects will include the treatment group (between-participant factor) and the visit (within-participant factor). The unstructured covariance matrix is preferred for this analysis. If the model does not converge, the “best” covariance structure will be chosen based on Akaike’s Information Criteria²³.

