7.8 Multiple Comparisons/Multiplicity

The primary efficacy analysis involves a single hypothesis test at the 2-sided significance level of 5%. A hierarchical testing procedure will be applied to secondary efficacy analyses to control the overall type I error rate. In the case that the primary efficacy analysis is statistically significant, the secondary efficacy endpoints will be tested at a 2-sided type I error rate of 0.05 in the order listed below. If any of the secondary endpoints are found to be not statistically significant at the 2-sided 0.05 level, the hypothesis testing will stop. Later endpoint(s) will be summarized descriptively and p-values may be produced for descriptive purposes only.

- Mean change in aggregate sensitivity of microperimetry within the EZ line break area from the Baseline Visit through the Month 24 Visit
- Mean change in reading speed from the Baseline Visit through the Month 24 Visit

- Mean change in the National Eye Institute Visual Function Questionnaire-25 (NEI-VFQ-25) near activities subscale score from the Baseline Visit through the Month 24 Visit

P-values produced for safety analyses and treatment group comparisons of demographic and baseline characteristics will be considered descriptive statistics that support the results of the primary efficacy analysis and not as formal tests of hypotheses.

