9.2 Secondary Efficacy Analysis

The secondary endpoints will be analyzed using the mITT Population and the PP Population to test for superiority of NT-501 implant over sham. The secondary endpoints are listed below:

- Mean change in aggregate sensitivity of microperimetry within the EZ line break area from the Baseline Visit to the Month 24 Visit
- Mean change in reading speed from the Baseline Visit to the Month 24 Visit
- Mean change in the National Eye Institute Visual Function Questionnaire-25 (NEI-VFQ-25) near activities subscale score from the Baseline Visit to the Month 24 Visit

The observed change from Baseline visit to the Month-24 visit will be compared using t-tests. The analyses will be based on the actual values observed at the Baseline and the Month-24 visit efficacy assessment, regardless of timing of the visit as long as it occurs within +/- 30 days for pre-COVID period or within +119 days post-visit timepoint for COVID-related delays. The estimated mean treatment effect, a 95% confidence interval (CI), and a 2-sided p-value will be provided. No imputation of missing data will be done.

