14.2 Appendix B: Overview of Planned Efficacy Analysis

Efficacy Endpoint		Endpoint Type¹	Population	Analysis Period	Subgroup Analysis	Sensitivity Analysis	Figure	Analysis Model
OCT	Rate of change in EZ Area Loss	1 ¹	FAS, PPS	24	Yes ²	Yes	Yes	Random Intercept Model
Microperimetry	Aggregate Sensitivity	2 ²	FAS, PPS	24	Yes ²	Yes ³	Yes	MMRM
IREST	Reading speed (words/min)	2 ²	FAS, PPS	24	Yes ²	Yes ³	Yes	MMRM
NEI-VFQ-25	Near activities subscale score	2 ²	FAS, PPS	24	Yes ²	Yes ³	Yes	MMRM

1 Indicates endpoint category, 1¹ = primary and 2² = secondary

2 Subgroup Analysis: Age at baseline, baseline endpoint measure

3 Sensitivity Analysis limited to impact of COVID-19

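### The gated secondary endpoints are tested on change with no baseline covariate in any of the three conflicting model descriptions: a possible loss of precision, not a bias

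*SAP*

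**What the plan says.** The documents describe the confirmatory secondary analysis in three ways.

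- **SAP 9.2:** "The observed change from Baseline visit to the Month-24 visit will be compared using t-tests". One sentence covers aggregate microperimetry sensitivity, IReST reading speed and NEI-VFQ-25 near activities. No covariate is named, and on missing values the section adds: "No imputation of missing data will be done". The sensitivity analyses in SAP 9.2.1 deal only with visit timing.
- **Protocol 12.3.2:** "Continuous secondary outcomes will be analyzed using a longitudinal mixed effects model", and the "fixed effects will include the treatment group (between-participant factor) and the visit (within-participant factor"). The treatment difference is read at 24 months. No baseline term is listed.
- **SAP Appendix B:** MMRM for all three endpoints, without a list of model terms. The baseline endpoint measure appears only as a subgroup factor.

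SAP 7.4 declines baseline adjustment for the primary analysis and otherwise offers exploratory covariate models. It says nothing specific about the confirmatory secondary tests.

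On multiplicity, SAP 7.8 says that after a significant primary result "the secondary efficacy endpoints will be tested at a 2-sided type I error rate of 0.05 in the order listed below": microperimetry, then reading speed, then near activities. It continues: "If any of the secondary endpoints are found to be not statistically significant at the 2-sided 0.05 level, the hypothesis testing will stop".

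**The concern.** Microperimetry and reading speed are both measured at baseline, and Protocol 7.1 makes reading speed monocular, so a study-eye baseline value exists. A change score subtracts the whole of that value, whereas ANCOVA subtracts only the part that predicts Month 24. Where the slope of Month 24 on baseline is below 1, the change score carries avoidable noise.

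The hierarchy raises the stakes. Imprecision at microperimetry lowers the chance that reading speed is tested at all, and imprecision at reading speed does the same for near activities. The documents state no power, SD or effect assumption for any secondary endpoint. The plan already uses the principle elsewhere: SAP 9.1.1 gives the primary endpoint a sensitivity model adjusted for baseline EZ area and age, and the secondary endpoints have no counterpart.

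**Working it through.** **The plan's own figure.** The only sample-size result is for the EZ-area slope (Protocol 12.2, SAP 5): m = 2(1.960 + 0.842)² × 0.0256 × (1 − 0.6) / (5 × 0.47 × 0.037²) = 49.97, so 50 per arm, raised to 56. It reproduces, but its correlation of 0.6 belongs to EZ area and cannot be carried over to reading speed or microperimetry.

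**Variance comparison.** Let S0 and S24 be the Baseline and Month-24 SDs and r their correlation.
- Change score, variance per participant: S0² + S24² − 2·r·S0·S24.
- ANCOVA, residual variance: S24²(1 − r²).
- Difference: (S0 − r·S24)². This is never negative, and it is zero when the slope r·S24/S0 equals 1.
- With S0 = S24 the ratio of ANCOVA to change-score variance is (1 + r)/2: 0.75 at r = 0.5, 0.85 at 0.7, 0.90 at 0.8, 0.95 at 0.9.
- With S24/S0 = 1.25 and r = 0.8 the slope is 1.25 × 0.8 = 1 and the ratio is 1.00, so there is no gain.

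**Reading speed, inputs.** Protocol 1.1 reports of Phase 2: "There was a significant difference between treatment groups in reading speed at 24 months (13.5 words read per minute", with p = 0.016), from 99 eyes randomized 1:1, or 49.5 per arm. The sidedness of this p is not stated, so both readings are shown.
- 2-sided: z = 2.409, SE = 13.5/2.409 = 5.60, SD of change = 5.60/√(2/49.5) ≈ 27.9.
- 1-sided: z = 2.144, SE = 13.5/2.144 = 6.30, SD of change ≈ 31.3.

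**Power** for m per arm = Φ(13.5 / [SD × √(2/m) × √((1 + r)/2)] − 1.96). The last square root is omitted for the t-test. Example at 56 per arm, p 2-sided: SE = 5.60 × √(49.5/56) = 5.27 and 13.5/5.27 = 2.56. The t-test has Φ(0.60) = 72.6%. ANCOVA at r = 0.5 has Φ(2.56/0.866 − 1.96) = 84.1%.

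| p read as, per arm | t-test | ANCOVA r = 0.5 | r = 0.7 | r = 0.8 | r = 0.9 |
|---|---|---|---|---|---|
| 2-sided, 56 | 72.6% | 84.1% | 79.4% | 77.1% | 74.8% |
| 1-sided, 56 | 62.6% | 75.0% | 69.6% | 67.2% | 64.8% |
| 2-sided, 50 | 67.8% | 79.8% | 74.7% | 72.3% | 70.0% |
| 1-sided, 50 | 57.7% | 70.1% | 64.7% | 62.2% | 59.9% |

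At 56 per arm the gain is 11.5 to 12.4 points at r = 0.5, about 4.5 at r = 0.8 and 2.2 at r = 0.9. A simulation at 50 per arm with an SD of change of 27.9 gave 66.9% against 71.2% at r = 0.8, and 67.4% against 68.8% at r = 0.9, which agrees in direction and rough size.

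**Which r is plausible.** With equal variances, an SD of change of 27.9 implies a between-person SD of 27.9/√(2(1 − r)): 28 words per minute at r = 0.5, 36 at 0.7, 44 at 0.8 and 62 at 0.9. The documents do not say which applies.

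**Microperimetry.** Protocol 1.1 says mean sensitivity did not differ between Phase 2 arms and that an aggregate comparison did, but gives no effect size, SD or correlation. No power figure can be formed.

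**The case against.** **The t-test is not the settled method.** This stands. Appendix B's MMRM is unspecified rather than shown to be unadjusted. Protocol 12.3.2 does not say whether baseline is one of the modelled visits, which bears on how far that model already uses baseline information. What the documents support is that no version lists a baseline covariate.

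**The Phase 2 back-calculation is fragile.** This stands too. Protocol 1.1 does not give the method behind p = 0.016. If it was adjusted or used pairing, 72.6% is not the t-test's power. Pairing was common: 99 − 67 = 32 participants contributed both eyes, in opposite arms where both were eligible (SAP 5.1.1).

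**The larger gains need a low r.** An r of 0.5 requires only 28 words per minute of spread between people who read in different languages. Stable differences between people push r up and the gain down.

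**Chance imbalance.** A reader might infer from the unrestricted, unstratified randomization that the t-test is biased. It is not: under 1:1 randomization the comparison of changes is unbiased and its type I error is controlled. Chance imbalance is part of the variance already counted above.

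**Exploratory adjustment is planned** in Protocol 12.1 and SAP 7.4, and Appendix B plans a subgroup analysis by baseline measure. Neither alters the confirmatory test.

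**Conclusion.** The point holds as one of efficiency. No description of the secondary analysis lists the baseline value as a covariate. In large samples ANCOVA is never less precise than the change score, and the data are already collected.

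The size is uncertain. The reading-speed gains of about 2 to 12 points assume r between 0.5 and 0.9, equal variances, independent Phase 2 eyes, an unadjusted Phase 2 comparison and full evaluability at 56 per arm. At the upper end of that range of r, or with a slope on baseline near 1, the gain is small or nil.

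A reader might also infer a demonstrated power loss at the first gate. The documents do not support that. They give nothing from which to size a microperimetry loss, and equal variances cannot be presumed for sensitivity measured within a lesion that the protocol describes as enlarging. Nor is it right to say that lost precision blocks later endpoints; it lowers the chance of reaching them.

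**What to change.** Before database lock, state one confirmatory model for aggregate sensitivity and reading speed, in the same terms, in SAP 9.2, SAP Appendix B and Protocol 12.3.2:

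- ANCOVA of the Month-24 change on treatment, with the study eye's baseline value of that measure as covariate; or MMRM with treatment-by-visit, baseline and baseline-by-visit terms.
- Its estimate, 95% CI and 2-sided p-value decide the gate.
- The unadjusted t-test becomes a sensitivity analysis.
- State the model for NEI-VFQ-25 near activities in the same edit, since the same SAP sentence governs it.

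ANCOVA costs one degree of freedom and needs no new data. Editing SAP 9.2 alone would leave the other two places in conflict with it, so the protocol text must change as well, and Protocol 16 handles permanent changes by amendment. The three descriptions need reconciling in any case, so the baseline term adds little further work.

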9.2.1 Sensitivity Analysis of Secondary Endpoints

- Exclusion of out of window visits: An analysis will be conducted excluding any out of window visits occurring more than +/- 30 days outside of the planned timepoints. Time-adjusted analysis: Time-adjusted analysis will be performed by adjusting the actual efficacy assessment results to the nominal timepoint, as described in Section 7.5.

9.3 Exploratory Efficacy Analyses

Any post hoc, exploratory analyses completed to support planned study analyses, which were not identified in this SAP, will be documented and reported in appendices in the CSR. Any results from these unplanned analyses will also be clearly identified as such in the text of the CSR.

10 SAFETY EVALUATION

All safety analyses will be performed for the Safety population. Each analysis will consist of a summary of data within each treatment group and overall.

Safety analyses will be performed on all participants who underwent either implant surgery or the sham procedure. The assessment of safety will be based on the summary of ocular and non-ocular treatment-emergent AEs (TEAEs) and ophthalmic examinations.

Safety analysis will include the Month 24 safety analysis, i.e. the set of data associated with the period from surgery through the Month 24 Visit.

The overall safety profile of the NT-501 implant versus sham will be assessed in terms of the following safety and tolerability endpoints:

- Incidence of treatment-emergent adverse events (TEAEs)
- Visual acuity
- Intraocular Pressure (IOP)
- Pupil Size

10.1 Treatment-Emergent Adverse Events (TEAEs)

The collection period of adverse events, serious and non-serious, will begin after surgery and continue throughout the course of the participant's participation in the study. For analysis purposes, all adverse events will be classified as TEAE.

The TEAEs will be presented by treatment group (NT-501 implant versus sham). Summaries for TEAEs include the following: all TEAEs regardless of causality, treatment-related TEAEs, ocular TEAEs, treatment-related ocular TEAEs, TEAEs by intensity, serious adverse events (SAEs), and TEAEs leading to discontinuation from the study.

All TEAEs will be coded using the Medical Dictionary for Regulatory Activities (MedDRA).

The incidence of TEAEs will be summarized for each treatment group by system organ class and preferred term. If a subject reports the same AE more than once, then that subject will only be counted once in the summary of that AE, using the most severe intensity.

AEs will be summarized through Month 24 and through the end of the trial/Month 48:

- All ocular TEAEs;
- All non-ocular TEAEs;
- All ocular TEAEs by intensity;
- All non-ocular TEAEs by intensity;
- All ocular TEAEs by relationship to surgical procedure/device/CNTF;
- All non-ocular TEAEs by relationship to surgical procedure/device/CNTF;
- Ocular SAEs;
- Non-ocular SAEs;
- Ocular SAEs by relationship to surgical procedure/device/CNTF;
- Non-ocular SAEs by relationship to surgical procedure/device/CNTF;
- Deaths; and
- Ocular/Non-ocular TEAEs that led to explantation of IP.

All SAEs and TEAEs leading to premature withdrawal from the study will be listed.

Summaries will be presented using frequency counts and percentages (i.e., the number and percentage of study eyes/participants with an event as well as the total number of events). Study eyes/participants with multiple occurrences of the same AE or a continuing AE will be counted once, and only the maximum severity level will be presented in the severity summaries, and the worst/highest relationship level in the relationship summaries. A separate table will summarize all TEAEs when each of them is considered unique, hereafter referred as AE count table. In addition, a listing containing individual participant adverse event data for all deaths and serious adverse events will be provided, separately. All adverse events will be presented in individual subject data listings.

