4. STUDY PLAN

4.1 STUDY DESIGN

This is a Phase 3, prospective, multicenter, masked, sham-controlled study of approximately 112 study participants with MacTel.

All participants are to be followed through the 24-Month Visit, where 1 month is defined as 30 days. Originally the subset of participants enrolled early into the study were to be followed through a 36-Month Visit and/or a 48-Month Visit, based on the date of the surgical procedure. The rate of change in the EZ (IS/OS) area loss over the Month-36 and Month 48 time points were identified as secondary endpoints. A decision has been made to discontinue the Month-36 and Month 48 study visits because the limited number of subjects completing these

visits does not provide sufficient statistical power to demonstrate a treatment effect for these secondary endpoints. The Sponsor decision to terminate this study early is not related to any safety or any adverse event related to the study treatment or surgical procedures related to the implantation.

With the current protocol amendment, the changes to the study visit schedule include the following:

- (1) Subjects who will complete the Month-24 visit after 01 December 2021 will not complete their scheduled Month-36 and/or their Month-48 study visits. These study participants will exit the study when they complete the Month-24 visit.
- (2) Subjects who have completed the Month-24 visit and have Month 36 and/or Month 48 visits scheduled before or on 01 December 2021 will exit from the study after completing these scheduled visits.
- (3) Subjects who have completed the Month-24 visit and have Month 36 and/or Month 48 visits scheduled after 01 December 2021 will not complete these visits but will complete a safety check-in call and exit the study by 01 December 2021.

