4 INVESTIGATIONAL PLAN

4.1 Overall Study Design and Plan

This is a Phase III, prospective, multi-center, masked, sham-controlled study of approximately 112 study participants with MacTel. All participants will be followed through the 24-Month Visit where 1 month is defined as 30 days. A subset of participants will be followed through the 36-Month Visit and/or the 48-Month Visit, based on the date of the surgical procedure. The study will have a common end date which will be the date when the last enrolled participant completes 24 months of follow up, approximately August 2022. Therefore, not all participants will complete the 36- and/or 48-Month Visit.

All participants will have a screening period of up to 30 days. During that time, a single baseline image of the EZ lesion will be taken to establish eligibility and the study baseline. The EZ line break area for eligibility will be determined by the reading center. Images will be reviewed for quality and may be repeated if necessary and obtained within the screening period (30 days). Two independent masked readers will determine lesion area from a single acceptable image. If the 2 estimates of area are within 10% and at least 1 measure is ≥ 0.16 and ≤ 2.0 mm², the MacTel lesion will be deemed eligible. If the 2 readings differ by more than 10%, an arbitrating reader will estimate the area. If the third reading is within 10% of either of the first 2 estimates, then the third and selected primary readings will be used to establish eligibility. Baseline EZ area will be the mean of the 2 qualifying estimates.

The implant surgery/sham procedure in the study eye should be completed within 4 weeks of randomization and/or up to 58 days from screening. Only 1 study-eligible eye of each participant will be designated as the study eye. Participants will be randomized (1:1) to receive the NT-501 implant or to undergo the sham procedure in the study-eligible eye. The implant surgery/sham procedure will occur on Day 0. Participants will be assessed on Day 1, Week 1 (± 2 days), Month 1 (± 7 days), Month 3 (± 14 days), Month 6 (± 30 days), Month 12 (± 30 days), Month 16 (± 30 days), Month 20 (± 30 days), and Month 24 (± 30 days). Note that, in regions other than France, a telephone contact will be made at Month 1 (± 7 days) and Month 3 (± 14 days) instead of a clinic visit. A subset of participants, based on the date of the surgical procedure, will be assessed at Month 36 (± 30 days) and Month 48 (± 30 days).

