7.3.3 Safety Set

The Safety Population will be defined as all participants who were randomized and received surgery (NT-501 implant or sham surgery) and have at least 1 safety measurement. Participants will be analyzed according to the group according to the treatment received, and no participants (or data) will be excluded from this dataset because of protocol violations that occur during the study. All analyses of safety will be conducted using the Safety Set.

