8 STUDY PARTICIPANTS

8.1 Disposition of Participants

Number and percentage of participants in the following categories will be summarized as appropriate:

- Randomized and received surgery (FAS)
- Randomized, Received Surgery and at least one safety measurement (Safety Set)
- Included in the PPS
- Prematurely discontinued in the study during the Treatment or Extension Periods and the reasons for discontinuations

A time to premature discontinuation analysis using the Kaplan-Meier method will be provided to assess the comparability of treatment groups in terms of premature discontinuation.

The disposition summary and discontinuation analysis will be based on the mITT Population.

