14.3 Appendix C: Overview of Planned Safety Analysis

Safety Endpoint		Analysis Period	Subgroup Analysis
AE	Ocular SOC and PT	24	No
	Non-Ocular SOC and PT	24	No
	Ocular by intensity	24	No
	Non-Ocular by intensity	24	No
	Ocular by relationship to surgical procedure/device/CNTF	24	No
	Non-Ocular by relationship to surgical procedure/device/CNTF	24	No
	Ocular SAEs	24	No
	Non-Ocular SAEs	24	No
	Ocular SAEs by intensity	24	No
	Non-Ocular SAEs by intensity	24	No
	Ocular SAEs by relationship to surgical procedure/device/CNTF	24	No
	Non-Ocular SAEs by relationship to surgical procedure/device/CNTF	24	No
	Deaths	24	No
	Explantation of IP	24	No

Safety Endpoint	Analysis Period	Subgroup Analysis
Visual Acuity	24	No
15 letter or more decrease from baseline		
Ophthalmic Examination	24	No
Change in IOP		
Change in pupil size	24	No
Development of CNV Shift	24	No
Explant/Sham Site Examination	24	No
Fluid leakage Shift	24	No
Subconjunctival hemorrhage Shift	24	No
Fibrosis Shift	24	No
Extrusion of device Shift	24	No
Vitreous inflammation Shift	24	No
Tractional retinal detachment Shift	24	No
Sectorial lens opacification Shift	24	No
Intraocular hemorrhage Shift	24	No
High or low intraocular pressures Shift	24	No
Dry eye Shift	24	No
Change in dark adaptation (per participant perception) Shift	24	No
Miosis (per participant perception) Shift	24	No
Persistent chemosis Shift	24	No
Scleral leak Shift	24	No

Note: All safety analyses are descriptive in nature; analysis is based on the Safety Set.

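### End-of-trial/Month 48 adverse event percentages in SAP 10.1 rest on follow-up cut by calendar date, so read as long-term incidence they understate the 48-month risk of late events

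*SAP*

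**What the plan says.** SAP 10.1 sets two reporting periods: "AEs will be summarized through Month 24 and through the end of the trial/Month 48". Both are presented in the same way: "Summaries will be presented using frequency counts and percentages", explained as "the number and percentage of study eyes/participants with an event as well as the total number of events". The population comes from SAP 7.3.3: "All analyses of safety will be conducted using the Safety Set". No separate denominator is given for the period after Month 24. The only time-to-event method in the SAP is for disposition (section 8.1): "A time to premature discontinuation analysis using the Kaplan-Meier method will be provided".

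Protocol 4.1 (version 7.0) has three exit rules:

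1. Participants whose Month 24 visit falls after 01 December 2021 leave at that visit.
2. Those past Month 24 with a Month 36 or 48 visit due on or before that date attend it and then leave.
3. Those past Month 24 whose later visits fall after that date "will not complete these visits but will complete a safety check-in call and exit the study by 01 December 2021".

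The protocol describes the participants completing Months 36 and 48 as limited in number and gives no count.

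SAP 4.1 still has a common end date of about August 2022, and adds: "Therefore, not all participants will complete the 36- and/or 48-Month Visit". Other parts of the SAP stop at Month 24: the scope in the Preface, the safety endpoints in 3.2.2.2, and Appendix C, where every row (for example "Ocular SAEs by relationship to surgical procedure/device/CNTF") carries an analysis period of 24.

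**The concern.** A percentage with the whole Safety Set as denominator counts a participant who left at Month 24 as event-free for the next two years, although nobody observed those years. SAP 10.1 calls these summaries incidence and attaches Month 48 to them, so a reader may take them as 48-month risks.

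The device is meant to stay in the eye for the duration of the study (Protocol 8.3). Appendix C tracks findings such as device extrusion, vitreous inflammation and development of CNV. If events of this kind can arise late, a crude end-of-trial percentage makes the absolute long-term risk look smaller than the data support. The SAP also disagrees with itself on whether a Month 48 safety period exists, so two programmers could produce different table sets from it.

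**Working it through.** The plan states no long-term adverse event figure, so there is none to reproduce. The check covers who can have follow-up beyond Month 24, and what a crude percentage then shows.

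**Inputs from the documents**
- One month is 30 days (Protocol 4.1, SAP 4.1), so Months 24, 36 and 48 are days 720, 1080 and 1440.
- The cut-off is 01 December 2021 (Protocol 4.1).
- The last participant reaches Month 24 in about August 2022 (SAP 4.1). Subtracting 720 days puts the last surgery between about 11 August and 10 September 2020; 25 August 2020 is used.
- There are about 112 participants, allocated 1:1.

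**Not given, so assumed**
- Accrual is uniform, with the first surgery between 1 September 2017 and 1 December 2018.
- The hazard is constant, unless stated otherwise.
- Check-in calls take place either on 01 December 2021 or, at the early extreme, by 31 August 2021 (the date of protocol version 7.0), but never before Month 24.

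**Step 1: surgery dates that allow each visit by the cut-off**
- Month 48: 01 Dec 2021 − 1440 days = 22 Dec 2017 or earlier.
- Month 36: 01 Dec 2021 − 1080 days = 17 Dec 2018 or earlier.
- Surgery after 01 Dec 2021 − 720 days = 12 Dec 2019 means exit at Month 24.

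These are nominal dates. The ±30-day windows, and the +119-day COVID window for Month 24, make them approximate.

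**Step 2: follow-up under the assumed accrual**
- 24–55% exit at Month 24.
- 57–97% exit before Month 36.
- 0–10% reach Month 48.

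Under the SAP's August 2022 end date, 43–67% would reach Month 36 and 0–34% Month 48. The outdated SAP text therefore matters for how these tables read.

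**Step 3: crude percentage against 48-month risk**

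With 24-month risk p, the risk to month t is 1 − (1 − p)^(t/24). The crude percentage is the average of this over participants' actual follow-up.

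Worked example: 75% followed to Month 24, 20% to Month 36, 5% to Month 48, and p = 0.20.
- Crude: 0.75 × 0.200 + 0.20 × (1 − 0.8^1.5) + 0.05 × (1 − 0.8²) = 0.150 + 0.057 + 0.018 = 0.225.
- 48-month risk: 1 − 0.8² = 0.360.
- Ratio: 0.225 / 0.360 = 0.62.

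Over the accrual scenarios of Step 2:

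| 24-month risk | Crude, end of trial | 48-month risk | Crude / 48-month |
|---|---|---|---|
| 5% | 5.4–7.1% | 9.8% | about 0.55–0.73 |
| 20% | 21.6–27.1% | 36.0% | about 0.60–0.75 |

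**Step 4: other event timings, with the 75/20/5 mix**
- Event possible only after Month 24, with 10% risk over Months 24–48: crude = 0.20 × (1 − 0.9^0.5) + 0.05 × 0.10 = 0.0103 + 0.0050 = 1.5%, against 10%.
- Event confined to the first months after surgery: everyone is observed over the risk period, so crude equals the 48-month risk.

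**Step 5: between arms, same mix, 24-month risks of 20% and 10%**
- Crude: 22.5% and 11.4%, giving a ratio of 1.98 and a difference of 11 points.
- 48-month: 36% and 19%, giving a ratio of 1.89 and a difference of 17 points.

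**The case against.** The strongest reply is that SAP 10.1 never calls the second percentage a 48-month risk. It is an observed frequency to the end of the trial. SAP 4.1 says openly that not everyone reaches the later visits, and Appendix C calls all safety analyses descriptive. The same section also provides Month 24 tables, total event counts and individual listings, none of which the calendar exits distort. This stands: the percentages are correct as observed frequencies. What remains is that a table headed Month 48, without person-time or numbers at risk, does not let the reader see how little of that period was observed.

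A second reply is that the documents describe adverse events as mainly related to the implant procedure and mostly resolving within days (Protocol 1.1 and 1.2.4). For such events the shortfall is close to nil, and a constant hazard exaggerates it. This also stands. It is a reason to supplement the crude percentages rather than remove them, because a rate per participant-year dilutes front-loaded surgical events with late, quiet follow-up.

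A reader might infer that most participants leave at or soon after Month 24. The documents do not say so. They give no accrual dates or counts, and a participant under the third exit rule can stay for almost 12 months beyond Month 24. Exit before Month 36 for most participants is plausible under the accrual assumed here, but it is an inference. Nor do the documents say that late safety events were the reason for the later visits; the purpose given in Protocol 4.1 is the rate of EZ area loss at those time points.

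**Conclusion.** The point holds in a limited form. Followed as written, SAP 10.1 yields end-of-trial/Month 48 percentages over unequal, calendar-truncated follow-up, with no exposure-based companion. They lie below the 48-month risk for any event that can occur after Month 24.

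The range of 55–75% illustrates this under uniform accrual and constant hazard; it does not estimate the actual shortfall. The shortfall is larger for events that occur only late and absent for early procedural events. Because the same cut-off applies to both arms, absolute risks and risk differences are lowered much more than the ratio is altered.

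It would be going too far to conclude that the trial's safety results are biased. The Month 24 tables, the Month 24 safety endpoints and all efficacy tests are untouched by the calendar exits. The disagreement between SAP 10.1, the Preface, SAP 4.1, Appendix C and protocol version 7.0 needs no assumption and should be corrected in any case.

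**What to change.** First, decide whether an end-of-trial safety period exists, and make SAP 10.1, SAP 4.1, the scope in the Preface and Appendix C agree with the exit rules of protocol version 7.0. Deleting the end-of-trial/Month 48 period from 10.1 would be one consistent answer.

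If the end-of-trial tables stay:
- Label the crude percentages as observed frequencies over unequal follow-up, and do not head them as Month 48 incidence.
- Add, by arm, participant-years from surgery to study exit and exposure-adjusted first-event rates (participants with a first event divided by participant-years to first event or exit).
- For ocular SAEs and explantation, add Kaplan-Meier estimates by arm, censored at study exit, with numbers at risk at Months 24, 36 and 48.

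The cost is SAP wording and a few extra table programs. Adverse events are already recorded from surgery to the last visit (Protocol 10.1) and a Study Exit Form is completed. Onset dates are assumed to be available, since the Month 24 cut needs them too. Late estimates will be imprecise: with 25% reaching Month 36 and 5% reaching Month 48, the numbers are 112 × 0.25 = 28 and 112 × 0.05 ≈ 6 across both arms. Showing those numbers lets the reader judge how much the late data can support.
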